9.9.4 MCI Due to AD Event Description

In clinical practice, the diagnosis of MCI due to AD, like AD dementia, cannot be made solely by laboratory or other tests, but requires the judgment of a clinician who takes into account clinical, cognitive, and functional criteria that define the syndrome. The clinical diagnosis, as defined by the National Institute on Aging (NIA) and Alzheimer's Association (AA) in Albert et al., 2011 (reference given in protocol):

- Establishes clinical and cognitive criteria:
 - Cognitive concern reflecting a change in cognition reported by subject or informant or clinician (ie, historical or observed evidence of decline over time).

- Objective evidence of impairment in one or more cognitive domains, typically including memory (ie, formal or bedside testing to establish level of cognitive function in multiple domains).
- Preservation of independence in functional abilities.
- Not demented.
- Examines etiology of MCI consistent with AD pathophysiological process:
 - Rule out vascular, traumatic, medical causes of cognitive decline, where possible.
 - Provide evidence of longitudinal decline in cognition, when feasible.
 - Report history consistent with AD genetic factors, where relevant.

A cognitive test battery has been specifically constructed to help study Investigators identify individuals who are beginning to decline in their cognitive status and who can be accurately diagnosed with MCI due to AD. This test battery is summarized in the [Appendix D](#), and the individual instruments that comprise the battery are described in detail in Section 9.1.15 of the protocol.

Study Investigators use this cognitive test battery to assess subjects' cognitive status and consider the results of this battery, in combination with the findings from other subject- and project partner-reported instruments of functional change and laboratory findings, to determine diagnosis and further subject flow within the study (ie, send case for adjudication or not).

For the purposes of this clinical trial, the clinical framework described by the NIA/AA publication was operationalized through the incorporation of objective cutoff points to provide the Investigator's guidance for making the clinical diagnosis of MCI due to AD, as

Follows (Table 4.a in the protocol):

Operationalized Criteria for MCI due to AD

Establish clinical and cognitive criteria

- Clinical Dementia Rating (CDR) scale score of 0.5 **AND** one or more of the following:
 - Fails at least one of the two memory tests in the cognitive test battery (failure defined as an individual test score at or below -1.5 SD of the demographically corrected normative mean (a), and the score reflects a change from baseline).
 - Fails 2 or more of the 12 measures in the cognitive test battery, representing separate cognitive domains.
 - (Failure is defined as an individual test score at or below -1.3 SD (10th percentile) of the demographically corrected normative mean, and the score reflects a change from baseline).

Examine etiology of MCI consistent with AD pathophysiological process

- Rule out vascular, traumatic, psychiatric, and other proximal medical causes of cognitive decline.
- Continued evidence of cognitive impairment or continued decline on 6 month follow-up (ie, 2 consecutive study visits showing impairment). (b)

(a) Normative data will be available per language.

(b) It is not required that the two consecutive visits show an identical profile (ie, meeting any definition of MCI due to AD on two consecutive visits is acceptable for a subject to be forwarded for adjudication). Note that the two consecutive visits must contain non-missing determinations of MCI due to AD status in order to contribute to the determination of an adjudicated event of MCI due to AD.

The criteria for triggering possible cases for adjudication are provided in the appendix of the CIAC Charter. For purposes of triggering possible cases, the choice of tests to assess the cognitive domains differs slightly from the table in [Appendix D](#). In particular, the Executive Function domain is assessed using Trail Making Test Part B and digit span total (rather than digit span backwards). And the attention domain consists only of Trail Making Test Part A (and does not include digit span forward).

The CVLT-II memory test consists of 3 measures, two of which are important for purposes of triggering and for calculation of the composite score: Short-Delay Free Recall and Long-Delay Free Recall. Of those two CVLT-II measures, only Long-Delay Free Recall is used for inclusion/exclusion. For post-baseline visits, failure on either of the two measures indicates failure on the CVLT-II test.

As described in the protocol, at each scheduled visit after randomization (ie, every 6 months), outcomes indicating possible MCI or AD will trigger further evaluation at an unscheduled comprehensive medical follow-up visit which should take place within one month of the routine scheduled visit when one of the triggering outcomes was met. The CDR, which is not taken at regularly scheduled post-randomization visits, is one of the procedures which is completed at the unscheduled comprehensive medical follow-up visit.

The primary endpoint is met only on the second consecutive occurrence when the diagnosis of MCI due to AD is confirmed by the adjudication committee. The adjudicators will look at all the collective information sent by the investigative sites in order to confirm (or not) the diagnosis of MCI due to AD. Subjects who convert directly to an AD dementia diagnosis by the NIA/AA criteria (reference given in protocol) will also be considered toward the numerical count of events that determines the duration of the study.

Note that data collected at the EoS/EW visit will also contribute to the determination of primary efficacy events of MCI due to AD. Further details about the definition of an event of MCI Due to AD and the adjudication process are provided in the protocol and the CIAC Charter.

Event Times and Censoring Times

For purposes of analysis, the **event time** of a CIAC confirmed event of MCI due to AD is the time from the randomization date to the **date of the first scheduled visit of the two consecutive scheduled visits at which a subject was assessed with a clinical diagnosis and determined as an primary endpoint event by CIAC using the data from scheduled visit and the triggered unscheduled comprehensive medical follow up visits.**

For subjects whose first and only clinical assessment of MCI due to AD (or AD itself) corresponds to their last visit during the study (e.g., due to subject dropout) and determined by CIAC as an primary endpoint event, the **event time** of a CIAC confirmed event of MCI due to AD is the time from the randomization date to the **date of the scheduled visit.**

A subject who does not have an event of MCI due to AD (including AD itself) will be censored for that event at the date of last visit at which a case of MCI due to AD could have been assessed (i.e., the last regularly scheduled visit at which the cognitive battery was assessed or the last unscheduled comprehensive medical follow-up visit at which the CDR was assessed, whichever is later). For subjects who discontinue from the study prior to their first assessment of the cognitive battery or CDR, the date of last contact will be used as the censoring time. At the time of the futility analysis, a subject who has not discontinued from the study and has not had an event of MCI due to AD (or AD) will be censored for that event at the date of the last visit at which a case of MCI due to AD could have been assessed prior to the futility analysis clinical database cut date (ie, the last regularly scheduled visit at which the cognitive battery was assessed or the last unscheduled comprehensive medical follow-up visit at which the CDR was assessed prior to the futility analysis clinical database cut date, whichever is later).

For subjects who die during the trial, the date of death is considered a censoring time for the event of MCI due to AD (rather than as a component of the event of MCI due to AD itself).

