Appendix A Schedule of Study Procedures (continued)

	Screening Visit 1	Base-line Visit 2	Random-ization Visit 3	Double-Blind Treatment Repeated yearly				Unscheduled - CMFV (q) (v)	EoS / EW Visit (b) (j)	Follow-up Visit (c)
				3 (a)	6	9 (a)	12			
Study Month:	-4	-1	0 (Day 0)	3 (a)	6	9 (a)	12			EoS/EW+0.5
Visit Window (t):	Max Day -125	Max Day -35		±2 weeks	±2 weeks	±2 weeks	±2 weeks	Within approx. 30 days of trigger		
Efficacy (continued)										
GDS		X			X		X		X(u)	
ADCS-MCFSI		X			X		X		X(u)	
EQ-5D		X						X	X(u)	
SF-36		X						X	X(u)	
IQCODE		X			X		X		X(u)	
ADCS ADL-PI		X			X		X		X(u)	
NPI-Q		X						X	X(u)	
ADCS-RUI		X			X		X	X	X(u)	
CDR		X						X	X(u)	
ADCS-CGIC- MCI		X			X		X	X (u)	X(u)	

Footnotes are on the following page.

Excl=exclusion, Incl=inclusion.

- (a) Telephone contact (should be every 3 months between the semi-annual clinic visits for the life of the study).
- (b) EoS/EW Visit is an ad hoc visit that, for study completion, would take place as soon as possible after a regularly scheduled Study Visit, either after the CIAC has confirmed that the subject has reached the MCI due to AD primary endpoint event (or any other irreversible cognitive impairment or dementia) or after a subject has withdrawn prematurely from the study. In cases where the endpoint has been reached, the efficacy assessments will not need to be captured at this Visit.
- (c) Subjects will have a safety follow-up call 2 weeks after completion or withdrawal. Subjects who withdraw their consent should still be contacted for a safety follow-up call, but the contact should only be recorded in the medical records (and not in the [e]CRF), according to data protection regulations.
- (d) footnote deleted
- (e) Please refer to Section 10.2.1.3.
- (f) As part of the comprehensive medical follow-up evaluation to rule out other causes of dementia and confirm the clinical diagnosis of MCI due to AD (See section 6.2.4). An MRI scan is not required to be performed if a study related MRI scan was collected within 6 months of the CMFV. For subjects who have contraindications for the MRI procedure (such as unremovable ferromagnetic dental work, cardiac pacemakers, etc) a CT scan can be done instead.
- (g) DNA sample expected to be collected at this visit, but if necessary, may be collected at any visit after randomization.
- (h) Sites should make every attempt complete the cognitive test battery in the order of outlined in Section 9.1.17.

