9.1.3 Definition of Study Day and Study Visit Windows

A windowing convention will be used to determine the analysis value for a given study visit that applies to observed data.

Study Day -1 corresponds to the randomization date. Other study days are defined relative to Study Day 1, the date of first double-blind study drug dose. Relative day is calculated as (date of interest - date of first dose +1) for study days on or after the date of first dose and as (date of interest - date of first dose) for study days prior to the first dose date.

For each visit, a window will be defined such that the lower and upper bounds of each window is generally the midpoint between 2 consecutive study visits. The visit windows and applicable study day ranges are presented below in [Table 9.a](#).

Table 9.a Visit Windows

Nominal Visit Month	Nominal Visit Day	vMRI	Height, ECG, Chemistry and Hematology, PK, RU, DNA/RNA, PE	All Other Variables (c)
Baseline	-36 to -1 (a)	≤ -1	≤ -1 (b)	≤ -1
6	183			2—273
12	365		2—547	274—456
18	548			457—638
24	731	639—821	548—912	639—821
30	913			822—1003
36	1096		913—1277	1004—1186
42	1278			1187—1369
48	1461		1278—1643	1370—1551
54	1644			1552—1734
60	1826		1644—1917	1735—1917
66/Final (d)	2009	≥1370	≥1918	≥1918

(a) Consistent with SDTM dataset standards, date of first dose of double-blind study drug is defined as Day 1, and the day before is defined as Day -1. Per the protocol, date of first dose of dose of double-blind study drug is scheduled for the day after randomization. Exemptions were granted on a case-by-case basis for subjects who had a screening-to-randomization time frame greater than the 35-day window planned per the protocol.

(b) No baseline assessment for PK samples.

(c) CDR and NPI-Q are collected only at Baseline (Visit 2), unscheduled visits (eg, comprehensive medical follow-up visits) and End of Study / Early Withdrawal.

(d) The planned study duration of 5.5 years is approximate, since this is an event-driven trial.

For safety variables, visit windows are exhaustive and the lower and upper bounds of each window are the midpoints between the scheduled visit days for the current visit and the adjacent visits.

More than 1 result for a parameter may be obtained in a visit window. In such an event, the result with the date closest to the scheduled visit day will be used. In the event of 2 observations equidistant to the scheduled visit day, the later of the observations will be used.

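### SAP 9.9.4 lets the EoS/EW visit create a primary event but leaves it out of the list of visits that set the censoring date

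*SAP*

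**What the plan says.** SAP Section 9.9.4 states that "data collected at the EoS/EW visit will also contribute to the determination of primary efficacy events of MCI due to AD". Section 4.0, item 2, gives the reason: the data resemble those planned for the comprehensive medical follow-up visit (CMFV).

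Under Event Times and Censoring Times, the same section says that a subject without an event "will be censored for that event at the date of last visit at which a case of MCI due to AD could have been assessed". It then defines that visit, introduced by i.e., as the later of two kinds: "the last regularly scheduled visit at which the cognitive battery was assessed or the last unscheduled comprehensive medical follow-up visit", the second kind being one with a CDR. Subjects who leave before a first battery or CDR are censored at last contact, and deaths at the date of death.

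The EoS/EW visit fits neither listed kind:

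- Protocol Appendix A, footnote (b): "EoS/EW Visit is an ad hoc visit". Footnote (i) contrasts it with the previous regularly scheduled visit.
- SAP 9.9.4 on regular visits: "The CDR, which is not taken at regularly scheduled post-randomization visits". The CDR is collected at EoS/EW.
- SAP Table 9.a, footnote (c), places the post-baseline CDR at "unscheduled visits (eg, comprehensive medical follow-up visits) and End of Study / Early Withdrawal", naming EoS/EW apart from unscheduled visits.

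For a first and only diagnosis at a subject's last visit, Section 9.9.4 dates the event to the scheduled visit. It does not say which date applies when the diagnosis comes from EoS/EW data.

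**The concern.** A visit that can produce an event is a visit at which a case could have been assessed. The list therefore breaks the principle it is meant to define, and two programmers could build different primary time-to-event datasets from the same text.

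Take two subjects, both normal at Month 24, who leave at Month 28.5 and are tested at exit. If the first fails and is confirmed by the adjudication committee, an event is recorded. If the second is normal, censoring falls at Month 24 and 4.5 months of assessed event-free time are dropped. A subject who dies, by contrast, is credited with unassessed time up to death.

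A second gap concerns a subject whose only post-baseline assessment is a withdrawal visit at, say, Month 5. The last-contact fallback does not apply because an assessment was made, and no listed post-baseline visit exists. That assessment may still qualify the subject for the FAS (SAP 9.3).

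What is at stake is the derivation of the primary endpoint, the absolute conversion estimates used for biomarker qualification (SAP 9.9.10), and the last-negative dates used by the interval-censored analysis (SAP 9.9.3.3).

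**Working it through.** **Inputs (Protocol 13.3, SAP 8.0):** 5-year event rates 15% (placebo) and 9% (active); two-sided alpha 0.01; power 90%; 12% annual dropout; 1,173 per arm; 202 events. Clinic visits are 6-monthly (Protocol 6.1). At EoS/EW the battery is repeated only if more than 3 months have passed since the last regular visit, and the CDR only if more than 3 months have passed since it was last given (Appendix A, footnotes (i) and (u)).

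**Plan's own figures.** HR = ln(0.91)/ln(0.85) = 0.5803. Schoenfeld events = 4(2.576 + 1.282)²/[ln 0.5803]² = 201, against 202 stated. Five-year dropout = 1 − 0.88⁵ = 47.2%, against 47% stated. Both reproduce.

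**Follow-up lost under the literal list.** Dropout hazard = −ln(0.88) = 0.1278 per person-year. Assume withdrawals fall uniformly between 6-monthly visits and attend the exit visit.

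- Every withdrawal visit counts, mean gap 3 months: 0.1278 × 0.25 = 3.2% of person-time.
- Only the half falling more than 3 months after a visit count, mean gap 4.5 months: 0.1278 × 0.5 × 0.375 = 2.4%.

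**Subjects with no clear censoring date.** Expected withdrawals before Month 6: 1 − 0.88^0.5 = 6.2%, or about 145 of 2,346. Between Months 3 and 6, counting from randomization: 0.88^0.25 − 0.88^0.5 = 3.05%, or about 71. These are the subjects for whom the battery would be due at exit.

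**Treatment comparison.** Simulation with 1,173 per arm over 5 years, battery at exit only after more than 3 months:

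| Scenario | HR, literal list | HR, EoS/EW added |
|---|---|---|
| Planned effect, 12% dropout in both arms | 0.590 | 0.590 |
| True HR 1, dropout hazard 1.5 times on active | 1.0094 | 1.0092 |
| True HR 1, dropout hazard 2 times on active | 1.0149 | 1.0144 |

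In the first row the rejection rate is 0.885 under both rules, and about 5 of roughly 208 events are detectable only at exit.

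**Kaplan-Meier conversion.** Simulated placebo subjects, every early withdrawal assessed at exit, administrative end assumed at 4 to 5.5 years:

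| Rule | Year 4 | Year 5 |
|---|---|---|
| Literal list, exit events dated back to the last scheduled visit | 12.59% | 15.45% |
| Literal list, exit events dated at exit | 12.57% | 15.51% |
| EoS/EW added, exit events dated at exit | 12.56% | 15.49% |

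The largest gap from the corrected rule is 0.04 percentage points. If every completer's EoS visit also counted, it would be about 0.4.

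**Why so little.** Nearly all events are dated at 6-monthly visits. A subject who leaves between two visits is in the risk set at the first and out of it at the second, whichever censoring date is used. The restored time matters only for events dated between visits, which are those dated at exit.

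**The tail.** Suppose exit-diagnosed events are dated at exit while normal exits are censored at the preceding visit. Beyond the last scheduled visit of the longest-followed subjects, only exit-diagnosed subjects remain at risk. With m of them left, survival is multiplied by (m − 1)/m, then (m − 2)/(m − 1), and so on to zero. That fall is an artefact.

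**The case against.** The strongest reply is that the governing clause already covers an EoS/EW visit with battery or CDR, and that SAP 7.2.1.2 groups EoS/EW under scheduled visits. But that grouping is for change-from-baseline endpoints, whereas the censoring rule says regularly scheduled and defines its clause by a closed list. The sensible reading is available but not secured.

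It is also fair that a single diagnosis at exit may not become an event. Protocol 6.2.4 does not forward a first MCI diagnosis for adjudication, and SAP 9.9.4 generally requires a second consecutive occurrence. Section 9.9.4 does, however, provide for a committee-confirmed event at a last visit. How often that happens depends on the adjudication charter, which is not among the documents.

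A reader might infer a larger harm. Placing every exit, completers included, uniformly in the 6-month interval gives a loss of 6.2% of follow-up and a person-time event rate overstated by 1/(1 − 0.062) − 1 = 6.6%. The documents do not support this. Protocol Appendix A says the "EoS/EW Visit is an ad hoc visit that, for study completion, would take place as soon as possible after a regularly scheduled Study Visit", so completers should have little gap, and events per person-time is not a planned estimate. A reader might also infer that unequal withdrawal would bias the treatment comparison. In the simulation, dropout at twice the planned hazard on active moves the HR by only 0.0005.

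Finally, if exit events are dated back to the last scheduled visit, events and censoring share one scale, and a subject censored at that visit still counts in its risk set. The asymmetry then largely disappears, but the SAP does not say this is intended.

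**Conclusion.** The point stands as a minor internal inconsistency in the primary censoring rule: wrong as written. The list omits a visit type that the same section uses to determine events.

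The literal rule discards up to about 6 months of assessed event-free time per affected withdrawal, or about 2% to 3% of total follow-up. It also leaves no clear censoring date for subjects assessed only at a withdrawal visit before Month 6. The 202-event target is unaffected, and the effect on the hazard ratio and power is negligible. Kaplan-Meier estimates through Year 5 change by under about 0.1 percentage point for early withdrawals, with about 0.4 as an outer bound. Only the extreme tail can be visibly distorted, and only if exit events are dated at exit while normal exits are censored earlier.

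These sizes assume 12% annual dropout, exits uniform between exact 6-monthly visits, and attendance at the exit visit. Protocol 7.5 asks only for efforts to complete the withdrawal procedures, so the real loss is probably smaller.

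**What to change.** 1. In the SAP 9.9.4 censoring list, add a third kind of visit: *or the EoS/EW visit at which the cognitive battery or CDR was assessed*, taking the latest of the three. This also gives a date to subjects assessed only at an early withdrawal visit.
2. In the event-time paragraph, state which date applies to an event first diagnosed at EoS/EW, so that event and censoring times are on one scale. Once EoS/EW visits count for censoring, the matching choice is the EoS/EW date. It also fits the SAP's aim of dating onset to the visit where impairment is first noted (Section 4.0, item 1). If the preceding scheduled visit had itself raised the concern, the existing rule already gives that visit's date.
3. Carry the same dates into the interval-censored analysis.

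The futility-cut sentence needs no change, since it covers only subjects who have not discontinued.

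The cost is one phrase and one sentence in the SAP before unblinding. No new data, sample-size change or alpha cost is involved.

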7.5 Procedures for Discontinuation or Withdrawal of a Subject

The investigator may terminate a subject's study participation at any time during the study when the subject meets the study termination criteria described in Section 7.4. In addition, a subject may discontinue his or her participation without giving a reason at any time during the study. Should a subject's participation be discontinued, the primary criterion for termination must be recorded. In addition, efforts should be made to perform all procedures scheduled for the EW Visit. Discontinued or withdrawn subjects will not be replaced.

Subjects who discontinue study medication prematurely should be contacted by the study site every 6 months until the conclusion of the study via telephone to assess the general well-being of the subject as well as to obtain any changes in medications related to cognitive health. In the event the subject is not able to be reached, the subject's caregiver or primary care physician can be contacted to obtain this information.

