13.1.1 Analysis Sets

All efficacy and safety variables will be analyzed using the full analysis set (FAS). The FAS will consist of all randomized subjects. The per-protocol population will be described in the SAP.

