The sample size for this study is based on the event-driven analysis that is planned for comparing treatment groups within the high-risk stratum. For the purposes of this study, it is assumed that the placebo-treated non-Hispanic/Latino Caucasian subjects in the high-risk stratum will have an event rate of 15% over a 5-year period. This is more conservative than the 18% cited in the table, to assure adequate sample size. With an expected improvement of a reduction in event rate of 40%, the target event rate for the active treatment group will be 9% over 5 years. Furthermore, the following specifications are used: alpha=0.01, a 2-sided statistical test based on survival analysis, power=90%, annual dropout rate of 12% (or cumulative dropout rate of 47% over 5 years). In order to detect a difference of the specified magnitude ($\geq 40\%$ reduction in conversion rates over 5 years), at least 202 events must be observed during the course of the study in non-

Hispanic/Latino Caucasian subjects (primary analysis). Based on these assumptions and the fact that only non-Hispanic/Latino Caucasian subjects will be used for the primary analyses, a total of 2,346 non-Hispanic/Latino Caucasian subjects (1,173 on pioglitazone/1,173 on placebo) are required from the high-risk stratum for randomization.

Sample Size for the Phase 3 Study Based On Qualifying the Test Used to Stratify Subjects

While using data from the results of risk stratification and not a comparison between randomized groups, the same analysis as specified for comparing the treatment groups within the high-risk stratum will also be used to compare the two placebo groups (high-risk placebo and low-risk placebo). Thus, assuming that the placebo-treated subjects in the low-risk stratum will have a conversion rate of 4% over a 5-year follow-up period, then approximately 314 non-Hispanic/Latino Caucasian subjects identified as low-risk for the event are required in that stratum. While this number of subjects enrolled in the low-risk stratum will provide very high power (99% with $\alpha=0.01$) to validate the enrichment algorithm with the assumed 5-year conversion rates (ie, 15% vs. 4%).

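### SAP 9.9.4 censors deaths at the date of death without saying whether this overrides last-assessment censoring; the effect is small, but the rule should be aligned (minor)

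*SAP*

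**What the plan says.** SAP 9.9.4, under event and censoring times, has three rules for subjects without an event.

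- General rule: censor "at the date of last visit at which a case of MCI due to AD could have been assessed". This means the later of the last scheduled visit with the cognitive battery and the last comprehensive follow-up visit with the CDR.
- Deaths: "For subjects who die during the trial, the date of death is considered a censoring time for the event of MCI due to AD". The sentence goes on to say that death is not part of the event.
- Never assessed: "For subjects who discontinue from the study prior to their first assessment of the cognitive battery or CDR, the date of last contact" is the censoring time.

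The section does not rank the general rule against the death rule. It also does not say whether a death after withdrawal counts as a death during the trial, and it does not define last contact.

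Three other places bear on this.

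- SAP 9.9.3.1 and 9.9.3.2 run both primary Cox models on the FAS. SAP 9.3 admits only subjects with a usable post-baseline primary-efficacy value.
- Protocol 13.1.1 differs: "The FAS will consist of all randomized subjects". SAP 9.17 does not list this departure.
- Under Protocol 7.5, subjects who stop study drug early "should be contacted by the study site every 6 months until the conclusion of the study via telephone". The calls cover general well-being and medication related to cognition, with no cognitive testing.

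**The concern.** SAP 9.9.3.3 itself recognises that the onset of MCI due to AD is usually unobserved and is picked up only at a later visit. A subject is therefore known to be event-free only up to the last assessment. Censoring at death treats the interval from that assessment to death as observed and event-free.

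For a death on study the interval is at most about six months. For a subject who withdrew and whose death is learned of later, for example through the Protocol 7.5 calls, it can be longer. The arm or risk group with more such time has its event rate diluted, so a difference in mortality or drop-out can leak into the hazard ratio. The same rule feeds the efficacy comparison, the biomarker comparison and the futility look. Because precedence is not stated, two programmers could derive different censoring dates from the same text.

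**Working it through.** **1. The plan's own figure.** Protocol 13.3 says placebo "will have an event rate of 15% over a 5-year period" and that "the target event rate for the active treatment group will be 9% over 5 years", with two-sided alpha 0.01 and 90% power.

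- Hazard ratio = ln(0.91)/ln(0.85) = 0.580.
- Events (Schoenfeld, 1:1) = 4 × (2.576 + 1.282)² / (ln 0.580)² = 4 × 14.88 / 0.2962 = 201, against the stated 202.
- Power at 202 events is 90.2%.

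The formula contains no censoring date, so the target does not depend on this point.

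**2. Set-up.** Simulation with exponential event hazards -ln(0.85)/5 = 0.0325 and -ln(0.91)/5 = 0.0189 per year, the plan's 12% annual drop-out (deaths counted within it), 6-monthly assessments, five years of follow-up and the SAP FAS. The documents give no death rate. **Assumed:** 1%, 2% and 4% per year.

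**3. Extra person-time.** Share dying without an event × mean gap from last assessment to death, divided by person-years per subject up to the last assessment (placebo, about 3.357):

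| Annual mortality | On-study deaths only | Including deaths after withdrawal |
|---|---|---|
| 1% | 0.0302 × 0.248 / 3.357 = 0.2% | 0.039 × 0.604 / 3.357 = 0.7% |
| 2% | 0.0601 × 0.247 / 3.357 = 0.4% | 0.076 × 0.569 / 3.357 = 1.3% |
| 4% | 0.1214 × 0.247 / 3.357 = 0.9% | 0.147 × 0.509 / 3.357 = 2.2% |

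A separate run with fitted Cox models gave 0.4-0.7% and 1.5-2.2% for the two readings.

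**4. Hazard ratio.** The events do not change, so the rate ratio is multiplied by (1 + x_placebo)/(1 + x_pioglitazone), where x is the extra fraction of person-time.

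- Equal mortality and drop-out: the factor is 1 (simulated change at most 0.0001).
- Mortality 2% placebo, 3% pioglitazone, on-study deaths only: x = 3.3729/3.3579 - 1 = 0.45% and 3.3852/3.3626 - 1 = 0.67%. The factor is 1.0045/1.0067 = 0.998, so 0.5824 becomes 0.5811.
- Mortality 4% placebo, 2% pioglitazone, including deaths after withdrawal: 0.5801 becomes 0.5864, or +1.1%. Power at 202 events goes from 90.2% to 88.8%, the largest change among the cases run.
- Fitted Cox models with mortality or drop-out differing by arm gave shifts of about 0.3-1.6%.

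For on-study deaths alone, x is close to the death rate times a quarter-year gap (0.02 × 0.25 = 0.5%), whatever the drop-out. Unequal drop-out therefore matters mainly if deaths after withdrawal are dated at death.

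**5. Biomarker comparison.** Age is part of the risk algorithm, and the primary biomarker model in SAP 9.9.3.1 does not adjust for it, so unequal mortality is more plausible here. With assumed mortality of 3% against 1.5%, or 4% against 2%, the shift was under 1% and toward the null.

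**6. The last-contact sentence.** At 12% annual drop-out, 1 - 0.88^0.5 = 6.2% leave before Month 6.

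- SAP FAS: they are excluded and add no person-time.
- Protocol FAS, last contact taken as study exit: 3.3876/3.3723 - 1 = about 0.5% extra.
- Protocol FAS, last contact taken as telephone contact up to year 5: about 8-9% extra, together with the death rule.

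**The case against.** The best defence is that the death sentence serves another purpose. It establishes that death is a censoring reason and not an endpoint component, and nothing in it says that it displaces last-assessment censoring for someone already withdrawn. For on-study deaths the gap is short. Events are dated at scheduled visits, so a subject who dies between two visits has mostly left the risk set before the next cluster of event dates, and the person-time figures tend to overstate the effect on a Cox model. SAP 9.9.3.3 plans an interval-censored analysis of both primary comparisons, and the futility text already censors continuing subjects at the last assessable visit.

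Most of this stands, and it is why the point is minor. It does not settle which date a programmer should use. SAP 9.9.3.3 does not state the last event-free bound for deaths, so that analysis could inherit the same date.

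A reader might infer something stronger: that the last-contact rule credits years of telephone follow-up as event-free and moves the primary hazard ratio 5-7% toward the drug. The documents do not support that. The SAP FAS excludes these subjects. Last contact is not equated with the Protocol 7.5 calls, which are prescribed for subjects stopping medication, whereas the SAP sentence concerns leaving the study. The 5-7% also needs the protocol FAS and assumed annual drop-out of 16% on pioglitazone against 8% on placebo, where the plan uses a single 12%. The 6.2% itself is an upper bound, because an early-withdrawal visit can supply a battery or CDR.

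**Conclusion.** The point holds for deaths, as a minor inconsistency with the SAP's own general rule and an unstated order of precedence. Under the SAP FAS, assumed mortality of 2-4% a year gives about 0.4-2% extra unassessed person-time; the upper end requires deaths after withdrawal to be dated at death. The hazard ratio is unchanged with equal drop-out and mortality, and shifts by roughly 0.3-1.6% if either differs, in favour of the group with more unassessed time. All sizes rest on assumed death rates.

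The last-contact sentence is inactive in the primary analyses as the SAP defines them. It becomes a live problem only if the FAS conflict is resolved to the protocol's definition and last contact is taken to include telephone calls.

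**What to change.** In SAP 9.9.4, for the primary efficacy, biomarker and futility analyses:

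- Censor a subject who dies without an adjudicated event at the last visit with a cognitive battery or CDR.
- State that this rule takes precedence over the date of death, including for deaths learned of after withdrawal.
- Keep date-of-death censoring, or a competing-risk analysis, as a sensitivity analysis.
- When the protocol and SAP definitions of the FAS are reconciled, replace the last-contact sentence with censoring at randomization for subjects with no post-baseline assessment.

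The cost is a few sentences and one sensitivity run before unblinding. It needs no new data and leaves the 202-event target unchanged.
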